5.1 Imputation rules

5.1.1 Study drug

Missing/partial start date or end date of double-blind treatment will not be imputed.

5.1.2 AE date imputation

Partial AE start and end dates will be imputed. If there is uncertainty whether an AE occurred on-treatment or not, imputation will be performed, such that AE will be considered as on-treatment. Rules for imputing AE end date or start date will be provided in Programming Dataset Specification (PDS) document in details.

5.1.3 Concomitant medication date imputation

Rules for imputing the CM end date or start date will be provided in Programming Dataset Specification (PDS) document in details.

5.2 Visit windows

In general, if two consecutive visits V_t and V_s are x days apart, the upper limit of the visit window for V_t will be $V_{t+x/2}$ and the lower limit for the visit V_s will be $V_{s-x/2}$ (if x is even, the lower limit for V_s will be $V_{s-x/2}+1$, and the upper limit for V_t will be $V_{t+x/2}$). The algorithm needs to ensure that visit windows are not overlapping and that there are no gaps, such that each assessment can be uniquely allocated to one visit window.

For ECG and spirometry assessments, unplanned visits will be ignored for the windowing as scheduled timing is not available. If there are multiple assessments within a visit window with different scheduled time points, the one with the planned scheduled time points of the target day will be used; if scheduled time points are the same, the visit closer to the target day will be used.

For all other assessments, unplanned visits will also be considered for assigning visit windows. If there are multiple assessments within a visit window the closest to the target day will be used.

Only on-treatment values will be considered for mapping of visit windows. For trough FEV₁ visit windowing will be performed twice, once for primary analysis considering on-treatment measurements, and once for supportive analysis considering all post-baseline measurements whether being on-treatment or not.

The below table presents the visit windows for the respective assessments.

Analysis visit	Scheduled Day	Visit window – assessments a)	Visit window – assessments b)	Visit window – assessments c)	Visit window – assessments d)	Visit window – assessments e)
Day 1 post dose	Day 1	Day 1 (post-dose) - Day 7				

Week 2	Day 15	Day 8 - Day 22	Day 1 (post dose) - Day 22			
Week 4	Day 29	Day 23 - Day 43	Day 23 - Day 43	Day 2 - Day 43		
Week 8	Day 57	Day 44 - Day 71	Day 44 - Day 71	Day 44 - Day 71		
Week 12	Day 85	Day 72 - Day 99	Day 72 - Day 99	Day 72 - Day 99	Day 2 - Day 127	
Week 16	Day 113	Day 100 - Day 127	Day 100 - Day 127	Day 100 - Day 127		
Week 20	Day 141	Day 128 - Day 155	Day 128 - Day 155	Day 128 - Day 155		
Week 24	Day 169	Day 156 - Day 183	Day 156 - Day 183	Day 156 - Day 183	>Day 127	> Day 1
Follow-up	Day 197	>= Day 184	>= Day 184	>= Day 184		
a) ECG b) Vital signs c) Spirometry, Hematology, Chemistry, Urinalysis d) SGRQ, PGI-S, CASA-Q e) Weight, smoking status, XXXXXXXXXX						

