The study includes optional assessments such as the additional pharmacokinetic sampling timepoints at Day 1 and Day 15 [REDACTED]. As previously described, each additional data collection activity may not be conducted in all countries, depending on regulatory acceptability, logistic considerations, and need of participants for the respective activity. Any additional data collections require a separate signature, if the subject agrees to participate. It is required as part of this protocol that the Investigator presents the available options to the subjects, as permitted by local governing regulations. The process for obtaining consent should be exactly the same as described above for the main informed consent.

Declining to participate in 1 or more of these optional assessments ([REDACTED] additional pharmacokinetic sampling) will in no way affect the subject's ability to participate in the main research study.

A copy of the approved version of all consent forms must be provided to Novartis/sponsor after IRB/IEC approval.

Subjects might be asked to complete an optional questionnaire to provide feedback on their clinical trial experience (see [Section 8.5.4](#)).

8 Visit schedule and assessments

The assessment schedule table ([Table 8-1](#)) lists all of the assessments and indicates with an "X", the visits when they are performed. All data obtained from these assessments must be supported in the subject's source documentation.

Patients should be seen for all visits/assessments as outlined in the assessment schedule or as close to the designated day/time as possible. Missed or rescheduled visits should not lead to automatic discontinuation. Subjects who prematurely discontinue the study for any reason should be scheduled for a visit as soon as possible, at which time all of the assessments listed for the final visit will be performed. At this final visit, all dispensed investigational product should be reconciled, and the adverse event and concomitant medications recorded on the eCRF.

Below [Table 8-2](#) will describe the order and timepoints for all the timed assessments in all the visits scheduled. If the subject is participating in the additional PK timepoints at Day 1 and Day 15, refer to the [Table 8-3](#) for these visits.

[figure not shown]
[figure not shown]

Table 8-1 Assessment Schedule

Period	Screening	Run-In		Treatment									Follow-Up	Unscheduled

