Visit Name	Screening	Run-In 1	Run-In 2	Day 1	Week 2	Week 4	Week 8	Week 12	Week 16	Week 20	Week 24	PSW ¹	Follow-Up	Unscheduled
Days	-21	-14	1	1	15	29	57	85	113	141	169	-	197	-
Informed consent	X													
Demography	X													
Physical Examination	X										X	X		
Body Height	X													
Body Weight	X										X	X		
Vital Signs	X	X	X	(X) ⁵	X	X	X	X	X	X	X	X	X	
Medical history/current medical conditions ²	X													
COPD exacerbation history	X													
Smoking history	X													
Smoking status	(X) ³										X	X		
Inclusion/Exclusion criteria	X	X	X											
Concomitant medications	X	X	X	X	X	X	X	X	X	X	X	X	X	
Dispensation of rescue medication	X	X		X		X	X	X	X	X	X			
Dispensation of standard background triple therapy		X		X		X	X	X	X	X	X			
Dispensation of study drug				X		X	X	X	X	X				
Spirometry		X		X		X	X	X	X	X	X	X	X	
Spirometry Reversibility Test		X												

Period	Screening	Run-In		Treatment									Follow-Up	Unscheduled
Visit Name	Screening	Run-In 1	Run-In 2	Day 1	Week 2	Week 4	Week 8	Week 12	Week 16	Week 20	Week 24	PSW ¹	Follow-Up	Unscheduled
Days	-21	-14	1	1	15	29	57	85	113	141	169	-	197	-
Electrocardiogram (ECG) ⁴		X	X	X ⁵	X ⁶	X	X	X	X	X	X ⁶	X	X	
COPD Assessment Test (CAT) ⁷		X												
St. George's Respiratory Questionnaire ⁷			X					X			X	X		
Patients Global Impression of Severity Scale (PGI-S general question) ⁷			X					X			X	X		
Patients Global Impression of Severity Scale (PGI-S specific question) ⁷			X					X			X	X		
Cough And Sputum Assessment Questionnaire (CASA-Q) ⁷			X					X			X	X		
e-Diary - rescue medication use	from Day -21	X	X	X	X	X	X	X	X	X	until Day 169	until PSW		
e-Diary - EXACT Questionnaire ⁸		from Day -14	X	X	X	X	X	X	X	X	until Day 169	until PSW		

[figure not shown]

Period	Screening	Run-In		Treatment									Follow-Up	Unscheduled
Visit Name	Screening	Run-In 1	Run-In 2	Day 1	Week 2	Week 4	Week 8	Week 12	Week 16	Week 20	Week 24	PSW ¹	Follow-Up	Unscheduled
Days	-21	-14	1	1	15	29	57	85	113	141	169	-	197	-
Assessment of childbearing potential	S													
Pregnancy Test (serum) ¹⁰		X												
Pregnancy Test (urine) ¹⁰	X		X			X	X	X	X	X	X	X	X	
Hematology		X		X		X	X	X	X	X	X	X	X	
Clinical Chemistry ¹¹		X		X		X	X	X	X	X	X	X	X	
Urinalysis ¹²		X	X			X	X	X	X	X	X	X	X	
PK blood collection				X ¹³	X ¹³	X	X	X	X	X	X ¹³	X		X ¹⁴
PK Sub-group (serial PK sampling)				X ¹⁵	X ¹⁵									
Adverse Events	X	X	X	X	X	X	X	X	X	X	X	X	X	
Serious Adverse Events	X	X	X	X	X	X	X	X	X	X	X	X	X	

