- In case of confirmed $QTcF > 500\ \text{msec}$, as indicated in [Section 6.5.1.1](#).

Investigational drug can be temporarily interrupted as a response to the occurrence of adverse events that do not fulfil the requirements above described for permanent discontinuation (refer to [Section 6.5.1](#)).

If permanent discontinuation of investigational treatment occurs, the investigator should make a reasonable effort to understand the primary reason for the subject's premature discontinuation of investigational treatment and record this information.

The investigator must also contact the IRT to register the subject's discontinuation from investigational treatment.

If discontinuation occurs because treatment code has been broken, please refer to Emergency breaking of treatment code [Section 6.6.2](#).

Subjects who have their investigational treatment permanently discontinued should NOT be considered withdrawn from the study UNLESS they withdraw their consent (see withdraw of informed consent section). **Where possible, they should return for the assessments indicated** in the assessment schedule in [Table 8-1](#). If they fail to return for these assessments for unknown reasons, every effort (e.g. telephone, e-mail, letter) should be made to contact the subject/pre-designated contact as specified in the lost to follow-up section. This contact should preferably be done according to the study visit schedule. If the subject cannot or is unwilling to attend any visit(s), the site staff should maintain regular telephone contact with the subject, or with a person pre-designated by the subject. This telephone contact should preferably be done according to

the study visit schedule and at a minimum information on new/ concomitant treatments and adverse events /serious adverse events should be obtained.

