2.1.1.3 Post-baseline measurement

Post-baseline measurements are defined as those assessments after the first dose of double-blind treatment.

When change from baseline is of interest the following formula will be used for each scheduled visit and time-point where baseline and post-baseline values are both available:

Change from baseline = post-baseline value – baseline value.

If not stated otherwise for efficacy analyses on-treatment values are defined as values taken post-baseline but no later than 1 day after last dose of double-blind treatment. Off-treatment values are defined as post-baseline values taken more than 1 day after last dose of double-blind treatment.

For safety analyses other than adverse events (AEs), e.g. laboratory, ECG, vital signs, on-treatment values are defined as values taken post-baseline but no later than 30 days after last dose of double-blind treatment.

AEs will be considered as on-treatment if the event is starting on or after the time of first dose of double-blind treatment but not later than 30 days after last dose of double-blind treatment.

Details on calculation of post-baseline values are provided in the latter sections.

If not stated otherwise, visit-windows will be used for the data that is summarized by visit; they are based on the study evaluation schedule and comprise a set of days around the nominal visit day. For any assessment, there are the protocol defined scheduled visits around which visit windows were created to cover the complete range of days within the study. When visit windows are used, all visits will be re-aligned, i.e., they will be mapped into one of the visit windows. Details on calculation of visit windows will be provided in [Section 5](#).

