2.1.1.4 Handling early termination of the 450mg b.i.d arm

If not stated otherwise, all efficacy inferential analyses will not include the 450 mg dose due to early termination of the 450 mg b.i.d arm, resulting in very few or no data in some of the strata (covariates/factors in the model) during the later visits. All descriptive summaries will include the 450 mg b.i.d. dose.

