2.7 Analysis of secondary efficacy objective(s)

2.7.1 Secondary endpoints

No multiplicity adjustment will be carried out for secondary analyses described below. In addition, the treatment effect of QBW251 compared to placebo that would have been observed had all patients remained on their assigned treatment will be estimated. Only on-treatment data will be used.

All analysis of secondary endpoints will be performed on the FAS.

Missing data for any reason will not be explicitly imputed and will be handled by the respective mixed effects model which implicitly imputes missing data assuming MAR.

If not stated otherwise, in the 450mg dose will be excluded from all inferential statistics. Descriptive analyses will include all doses.

Details on statistical models are provided in [Section 5.7](#).

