2.7.1.1.3 Severity of symptoms from PGI-S

The PGI-S rates the severity of the respiratory symptoms and of cough and mucus. Shift tables will be used to compare baseline to Weeks 12 and 24 for each PGI-S value.

The PGI-S change from baseline will be analyzed using a proportional odds model for repeated measures with the same terms as for the MMRM analysis described in [Section 2.5](#) for the primary variable with the baseline PGI-S value replacing the baseline FEV₁ value. The estimated odds ratios will be displayed over time along with the associated 90% confidence intervals. For the proportional odds analysis, the change in severity scores will first be grouped into the categories below, for cough and mucus categories -5 and 5 will be added. Further groupings of the change categories (such as better, no change, and worse) may be performed prior to the proportional odds analysis, if the sample size for some of the categories are too small.

Change from baseline in severity score	Change category
-4	Very much better
-3	Much better
-2	Better
-1	Slightly better
0	No change
1	Slightly worse
2	Worse
3	Much worse
4	Very much worse

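### SAP 5.2 lets an early on-treatment withdrawal questionnaire (SGRQ, PGI-S or CASA-Q, from Day 2) be analysed as the Week 12 result when no value closer to Day 85 exists

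*SAP*

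**What the plan says.** **Windows.** In the SAP 5.2 table, column d (SGRQ, PGI-S, CASA-Q) sets Week 12 as Day 2 to Day 127 and Week 24 as anything after Day 127. The filter is: "Only on-treatment values will be considered for mapping of visit windows". For efficacy, SAP 2.1.1.3 says "on-treatment values are defined as values taken post-baseline but no later than 1 day after last dose of double-blind treatment". If several values fall in one window, the one nearest the target day is used. No minimum exposure is set and withdrawal-visit questionnaires are not excluded.

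**Collection.** After baseline, Protocol Table 8-1 schedules these questionnaires only at Week 12, Week 24 and the premature-withdrawal (PSW) visit. Protocol Section 8 asks for a visit as soon as possible after premature discontinuation of the study, "at which time all of the assessments listed for the final visit will be performed".

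**Target of estimation.** SAP 2.7.1 says that the treatment effect "that would have been observed had all patients remained on their assigned treatment will be estimated". It uses on-treatment data only and leaves missing values to the model under MAR.

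**Use.** Week 12 values enter the MMRMs for CASA-Q (SAP 2.7.1.1.2) and SGRQ (SAP 2.7.1.2), the SGRQ responder model, and the PGI-S proportional-odds model. For PGI-S, also: "Shift tables will be used to compare baseline to Weeks 12 and 24 for each PGI-S value".

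**The concern.** The Week 12 window opens 83 days before its target. A patient who withdraws on Day 10, having dosed that day, and completes the questionnaires has that score analysed as a 12-week outcome. In effect the early score is carried forward, although the SAP says that missing data are not explicitly imputed.

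One visit can also be given two dates. At a Day 30 withdrawal visit, spirometry falls in the Week 4 window (column c, Day 2 to Day 43) while the SGRQ is labelled Week 12. SGRQ Part 1 asks about the past 4 weeks (Protocol Appendix 12), so a form completed in the first four weeks of treatment partly describes the time before first dose.

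The symptom and quality-of-life objectives are set at Weeks 12 and 24 in a dose-selection study. If benefit builds up over time, such values pull the Week 12 difference toward a short-exposure effect. If on-treatment withdrawal differs between arms, the bias could go either way.

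**Working it through.** **1. Reproduce the column d limits.** Scheduled days are 85 and 169, so x = 84, which is even. Under the SAP 5.2 rule:
- Week 12 upper limit = 85 + 84/2 = 127.
- Week 24 lower limit = 169 − 42 + 1 = 128.

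Both agree with the table. The Day 2 lower limit arises because Week 12 is the first post-baseline visit for these instruments.

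**2. Compare with spirometry (column c).**

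| | Questionnaires, Week 12 | Spirometry, Week 12 |
|---|---|---|
| Window | Day 2–127 | Day 72–99 |
| Width | 127 − 2 + 1 = 126 days | 99 − 72 + 1 = 28 days |
| Days before target | 85 − 2 = 83 | 85 − 72 = 13 |

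Days 2 to 71 (70 days) count as Week 12 for the questionnaires but not for spirometry.

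**3. Pass example visits through the rules** (on-treatment if day ≤ last dose + 1).
- Visit Day 2, last dose Day 1: Week 12.
- Visit Day 20, last dose Day 19: Week 12.
- Visit Day 20, last dose Day 18: off-treatment, not used.
- Visit Day 128, last dose Day 128: Week 24.

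**4. Lower limit if Day 1 is treated as the neighbouring visit.** x = 85 − 1 = 84. The midpoint is Day 43, and the even-x lower limit is 85 − 42 + 1 = 44.

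**5. Illustrative size.** Inputs from the SAP sample size section: 854 patients (excluding 450 mg) and 20% dropout. Assumptions: constant hazard, Day 1 as time 0, and a share q of stoppers with an on-treatment questionnaire. The horizon H of the 20% is not stated, so two values are shown.

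Formulas:
- h = −ln(0.8)/H.
- P(stop before Day 44) = 1 − exp(−43h).
- Affected share = q × P(stop before Day 44).
- Week 12 values available = P(reach Day 85) + q × [1 − P(reach Day 85)].
- Mean elapsed fraction f = [1/h − 43/(exp(43h) − 1)]/84.
- Attenuation = (affected / Week 12 values) × (1 − f), with benefit accruing linearly to Day 85.

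H = 168: P(stop before Day 44) = 0.0555, P(reach Day 85) = 0.894, f = 0.254.

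| q | Affected | Of 854 | Attenuation |
|---|---|---|---|
| 0.10 | 0.0056 | 5 | 0.0056/0.905 × 0.746 = 0.5% |
| 0.25 | 0.0139 | 12 | 0.0139/0.921 × 0.746 = 1.1% |
| 0.50 | 0.0278 | 24 | 0.0278/0.947 × 0.746 = 2.2% |

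H = 84: P(stop before Day 44) = 0.1079, P(reach Day 85) = 0.80, f = 0.251.

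| q | Affected | Of 854 | Attenuation |
|---|---|---|---|
| 0.10 | 0.0108 | 9 | 0.0108/0.82 × 0.749 = 1.0% |
| 0.25 | 0.0270 | 23 | 0.0270/0.85 × 0.749 = 2.4% |
| 0.50 | 0.0540 | 46 | 0.0540/0.90 × 0.749 = 4.5% |

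The attenuation counts only values before Day 44.

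**6. What a Day 44 limit leaves.** With H = 168, P(stop before Day 72) = 1 − exp(−71h) = 0.0900. The share of stops before Day 72 that fall on Days 44 to 71 is (0.0900 − 0.0555)/0.0900, about 38%. Questionnaires from those days would still count as Week 12.

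**The case against.** **It is a consistent design choice.** SAP 5.2 requires windows without gaps, and the first post-baseline window also runs back to treatment start for vital signs, spirometry and weight. A reader might infer that column d breaks the half-interval rule or the on-treatment rule. It breaks neither: the upper limit reproduces, and an early on-treatment questionnaire is on-treatment data. That stands. It does not settle the matter, because the first spirometry window reaches back only 29 − 2 = 27 days from its target.

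**The reach is narrow.** A reader might infer that everyone who stops drug early is affected. Protocol 9.1.1 says otherwise: "Subjects who have their investigational treatment permanently discontinued should NOT be considered withdrawn from the study UNLESS they withdraw their consent". Their next scheduled questionnaire is normally off-treatment and not used. A genuine on-treatment Week 12 value also displaces an early one, through the nearest-to-target rule. Both points stand. They do not help the patient who withdraws early while on drug, who has no later value to select.

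**The effect is small.** If the true SGRQ difference were 4 points (an assumption; 4 is the responder threshold), attenuation of 0.5% to 4.5% is 0.02 to 0.18 points. This stands. The possible bias from differential withdrawal is not quantified.

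**Dropping early values has its own cost.** With two post-baseline visits, these patients may have no outcome left, and MAR then rests on baseline covariates alone. SAP 5.7.2 fits the responder model in PROC GENMOD; unweighted estimating equations generally need a stronger missingness assumption than MAR. This stands and belongs in the fix.

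**Conclusion.** The concern holds in a limited form. Followed as written, SAP 5.2 can label a questionnaire from the first days of treatment as the Week 12 result, which does not fit the effect that SAP 2.7.1 sets out to estimate. It applies only to on-treatment withdrawal questionnaires from patients with no on-treatment value closer to Day 85.

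The size is probably small: about 0.6% to 2.8% of patients if the 20% dropout accrues over 168 days, or 1.1% to 5.4% if it is reached by Week 12, with attenuation of roughly 0.5% to 4.5% across both. These figures rest on a constant dropout rate, assumed on-treatment shares of 10% to 50% and linear accrual of benefit. None of these comes from the documents, apart from the 20% itself.

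A reader might infer that the dose-response conclusion is at risk. It is not: primary FEV1 has its own narrower windows, and E-RS uses daily diary scores averaged by week. The endpoints affected are secondary and carry no multiplicity adjustment. A reader might also infer that the stopped 450 mg arm distorts the Week 12 comparisons. That arm is excluded from efficacy inference. Because "All descriptive summaries will include the 450 mg b.i.d. dose", its Week 12 summaries could contain early values, but nothing in the documents shows how many of those patients completed an on-treatment withdrawal questionnaire.

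**What to change.** In SAP 5.2, column d:

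1. Set Week 12 to Day 44 – Day 127, the lower limit given by the SAP's own even-x rule with Day 1 and Day 85 as neighbours. It continues from the Day 43 limit in columns a to c.
2. Add a category, Early (Day 2 – Day 43), listed but not analysed as Week 12, so that no gap arises and each assessment still has one window.
3. Keep Week 24 as after Day 127.
4. Because Day 44–71 values still count as Week 12 in the main analysis, add a sensitivity analysis using the column c windows (Day 72–99 and Day 156–183). It also drops on-treatment values from delayed visits (Day 100–127), so it should stay a sensitivity analysis.
5. Report by arm how many Week 12 values come from a withdrawal visit.
6. State the missingness assumption for the PROC GENMOD responder model separately from the MAR statement for the MMRM.

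**Cost.** SAP text, one extra analysis and one count table; no new data. A few patients lose their only post-baseline value, and the MMRM then relies on MAR given baseline covariates.

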5.3 AEs coding/grading

The MedDRA version which will be available at the time of database lock, will be used for the coding purpose of the adverse events.

5.4 Laboratory parameters derivations

The following table shows the direction of interest when analyzing worst case values in form of maximum and/or minimum post-baseline values. If the direction of interest is given as "High" the maximum value will be calculated and used as worst value, if the direction is given as "Low" the minimum value will be taken, and if it is given as "Low and high", both the minimum value and the maximum value will be calculated and presented in summary tables.

Table 5.4-1 Directions of interest for worst case value for laboratory parameters

Laboratory Parameter	Direction of interest for worst case value
A. Hematology	
Hemoglobin	Low
Hematocrit	Low
Erythrocytes	Low
WBC	Low and high
Basophils	High
Eosinophils	High
Lymphocytes	Low and high
Monocytes	High
Neutrophils	Low and high
Platelets	Low and high
B. Chemistry	
Albumin	Low
Alkaline Phosphatase	High
ALT/SGPT	High
AST/SGOT	High
Bilirubin Total	High
Blood Urea Nitrogen (BUN)	High
Creatinine	High
Gamma GT	High
Potassium	Low and high
Magnesium	Low and high
Calcium	Low and high
LDH	High
Phosphorus	Low and high
Sodium	Low and high
████	████
████████	████
HbA1c	Low and high

The following table shows the criteria for clinically notable laboratory values. Not all parameters have notable criteria defined:

Table 5.4-2 Clinical notable criteria for selected laboratory tests

Laboratory parameter (unit)	Lower bound of clinically notable range	Upper bound of clinically notable range
Hematology		
Hematocrit (v/v)		
Male	0.37	
Female	0.32	
Hemoglobin (g/L)		
Male	115	
Female	95	
Platelets (x10E9/L)	75	700
WBC (x10E9/L)	2.8	16.0
Chemistry		
Albumin (g/L)	25	-
Alkaline Phosphatase (U/L)	-	3xULN
ALT/SGPT (U/L)	-	3xULN
AST/SGOT (U/L)	-	3xULN
Bilirubin Total (mcmol/L)	-	34.2
BUN (mmol/L)	-	9.99
Creatinine (mcmol/L)	-	176.8
Gamma GT (U/L)	-	3 x ULN
Potassium (mmol/L)	3	6
Magnesium (mmol/L)	0.51	1.07
Sodium (mmol/L)	125	160

v = volume, ULN = upper limit of normal

Table 5.4-3 Notable liver function test values

Criterion
ALT > 3 x the upper limit of normal range (ULN) ALT > 5 x ULN ALT > 8 x ULN ALT > 10 x ULN ALT > 20 x ULN
ALT or AST > 3 x ULN ALT or AST > 5 x ULN ALT or AST > 8 x ULN ALT or AST > 10 x ULN ALT or AST > 20 x ULN
Total bilirubin > 1 x ULN Total bilirubin > 1.5 x ULN Total bilirubin > 2 x ULN Total bilirubin > 3 x ULN
ALP > 1.5 x ULN ALP > 2 x ULN ALP > 3 x ULN ALP > 5 x ULN
ALT or AST > 3 x ULN and total bilirubin > 1.5 x ULN ALT or AST > 3 x ULN and total bilirubin > 2 x ULN ALT or AST > 5 x ULN and total bilirubin > 2 x ULN ALT or AST > 8 x ULN and total bilirubin > 2 x ULN ALT or AST > 10 x ULN and total bilirubin > 2 x ULN ALT or AST > 20 x ULN and total bilirubin > 2 x ULN
ALP > 3 x ULN and total bilirubin > 2 x ULN ALP > 5 x ULN and total bilirubin > 2 x ULN
ALT or AST > 3 x ULN and Total Bilirubin > 2 x ULN and ALP < 2 x ULN (Hy's law)

ALT = alanine aminotransferase, AST = aspartate aminotransferase, ALP = alkaline phosphatase

When a criterion contains multiple laboratory parameters, the criterion will only be considered to have been met when all conditions occur within a 3-day window. A case where all criteria are met at a post-baseline time point will be considered as newly occurring if the criteria are not met at baseline and will be considered as worsening if the criteria are met at baseline and at least one component is worsening from baseline irrespective of whether the other(s) are better.

